NCT03496610

- **Study Title:**

Intraoperative surgical wound infiltration vs Quadratus Lumborum (QL) Block for post-operative pain control after nephrectomy in living donor kidney transplant patients.

- **Short Title:**

Surgeon infiltration QL block comparison

- **Research Abstract:**

The purpose of this study is to determine whether there is a difference between surgical site infiltration of local anesthetic versus ultrasound-guided truncal block ( Quadratus Lumborum, QL block). Current practice at Duke is to infiltrate local anesthetic at the end of surgery by the surgical team or request a member of the regional anesthesia division to provide a QL block.

Given that the administration of a QL block utilizes ultrasound to target a specific anatomical plane where the nerves providing sensation to the abdominal wall travel, we hypothesize that this approach will provide superior analgesia and improved morbidity when compared to direct injection of local anesthetic to the wound site.

We will utilize patients undergoing living donor nephrectomies since these are heavily screened and understood to be in excellent health thus eliminating potential confounding variables. These patients will be followed for 7 days after surgery and data will be collected pertaining to their total opioid consumption, pain scores, GI complications, and ability to return to normal pre-surgery physical function levels.

Both parametric and non-parametric data will be analyzed with the appropriate statistical tests. Patients risks will be the same as for patients undergoing donor nephrectomy who are not participating in the study.

- **Primary Objectives:**

The purpose of this study is to determine whether there is a difference between surgical site infiltration of local anesthetic versus ultrasound-guided truncal block (Quadratus Lumborum, QL block). Specifically comparing total 24h opioid consumption.

- **Secondary Objectives:**

The exploratory objectives are:

- Pain scores at which other time points post surgery- hourly for the first four hours, at 6 hours, 12 hours, 24 hours, and 48 hours
- GI complications (bloating, nausea/vomiting, constipation)
- Total use of PRN pain medication for a total of 7 days post surgery.

- **Purpose of the Study:**

The purpose of this study is to determine whether there is a difference between surgical site infiltration of local anesthetic versus ultrasound-guided truncal block ( Quadratus Lumborum, QL block)

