Intraoperatively, patients will be given general anesthesia with endotracheal intubation which is the standard of care for these types of procedures. Induction will be achieved with propofol, lidocaine, fentanyl and a non-depolarizing neuromuscular blocking agent. Maintenance will be achieved with sevoflurane. A total of 100 mcg of fentanyl will be given during the case, 25mcg at induction and 75mcg in incremental doses throughout the case at the discretion of the attending anesthesiologist. A one-time IV bolus of 10mg IV dexamethasone (will not be given in diabetic patients) will be administered at the beginning of the procedure. After the completion of the surgery the patient will either receive 266 mg of liposomal bupivacaine mixed with 50 mg non-liposomal bupivacaine infiltrated into the wound by the surgeon or they will get bilateral ultrasound guided Quadratus Lumborum blocks by the anesthesia team. At the conclusion of the case, full neuromuscular reversal will be given, patient will be extubated, and taken to the post-operative care unit (PACU).

Post operatively patients will receive Tylenol 650 mg PO Q6h, Gabapentin 100 mg PO Q8h, and Toradol 15 mg IV Q8h (for a total of 3 doses). Additionally, patients will have post-operative orders for supplementary pain control that include 25mcg IV fentanyl for breakthrough pain, Tramadol 25 mg PO Q6h for pain score of 4-6/10, and Tramadol 50 mg PO Q6h for pain scores 7-10/10.

Upon arriving to the PACU patients will be assessed to determine their level of pain as well as nausea/vomiting. Subjects' verbal pain scores (NRS 11), opioid consumption, and GI complications will be recorded hourly for the first four hours, at 6 hours, 12 hours, 24 hours, and 36 hours post-surgical intervention. 24h opioid consumption (IV morphine equivalents) will be calculated. On post op day 1 patients will be asked to ambulate a short distance of 50ft and we will record pain levels using the numerical pain score reported during this activity. After leaving the hospital patients will be contacted via telephone daily until post op day 7 and will be asked the same questions they were asked during their hospital stay to asses opioid consumption, nausea/vomiting events, and GI complications.

- **Selection of Subjects:**

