  - Volunteers that are illiterate, blind, or do not understand English will not be eligible for this study.
- Do you plan to obtain written consent for the conduct of research?

- Yes

- **Subject's Capacity to Give Legally Effective Consent:**

Patients who do not have the capacity to give legally effective consent will not be approached for participation in this study.

- **Study Interventions:**

After the completion of the surgery the patient will either receive 266 mg of liposomal bupivacaine mixed with 50 mg non-liposomal bupivacaine infiltrated into the wound by the surgeon or they will get bilateral ultrasound guided Quadratus Lumborum blocks by the anesthesia team. At the conclusion of the case, full neuromuscular reversal will be given, patient will be extubated, and taken to the post-operative care unit (PACU).

- **Risk/Benefit Assessment:**

Risks of this study includes the following:

- Risks of Bupivacaine Liposome Given as a Nerve Block:
  - Greater than or Equal to 10% (Common):
    - Nausea, fever, constipation
  - At Least 2% but Less than 10% (Uncommon):
    - Muscle twitching, taste disturbance, urinary retention, fatigue, headache, confusion, low blood pressure, high blood pressure, itching, sweating, rapid heart rate, anxiety, fall, temporary swelling, sensory loss, change in liver function tests, hiccups, respiratory depression, bruising
  - Less than 2% (Rare):
    - Arrhythmia, slow heart rate, impaired hearing, blurred vision, chills, skin infection, lung/respiratory infection, wound secretion, white blood cell count increase, joint pain and swelling, back pain, decreased mobility, muscle spasms, muscle weakness or pain, tingling, fainting, sedation, delirium, urinary incontinence, cough, difficulty breathing, blister, redness, rash, bruising, blood clots in extremities, decreased blood pressure when standing
- Risks of Bupivacaine Liposome Given Directly Into the Surgical Wound:
  - Greater than or Equal to 10% (Common):
    - Nausea, constipation, vomiting
  - At Least 2% but Less than 10% (Uncommon):
    - Fever, dizziness, temporary swelling, anemia, low blood pressure, itching, rapid heart rate, headache, insomnia, muscle spasms, back pain, tiredness
  - Less than 2% (Rare):

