A total of up to 50 participants will be enrolled in the study in order to get 7-day follow up data from 40 participants. Participants will be randomized equally between Surgical Field Block and Regional Anesthesia groups based on sample size calculation for a non-parametric Mann-Whitney Test with  $a=0.05$ ,  $b=0.8$ , difference in means=2, and effect size of 1.0. The sample size required for a non-parametric test will provide greater than 80% power if the data meet requirements for a parametric t-test (<https://www.stat.ubc.ca/~rollin/stats/ssize/n2.html>).

- **Data & Safety Monitoring:**

In accordance with federal regulations the PI will monitor for, review, and promptly report to the IRB and appropriate institutional officials, all unanticipated problems involving risks to subjects or others

that occur in the course of a subject's participation in a research study (45 CFR 46.103(b)(5)(i) and 21 CFR 56.108(b)(1)), all AE reports will be reported per the DUHS IRB policies. PI will be monitoring all AEs and submitting reports to the IRB per DUHS IRB policy.

- **Privacy, Data Storage, & Confidentiality:**

- Explain how you will ensure that the subject's privacy will be protected:
  - Potential subjects and their families will be approached private rooms. Any guests not involved in the consent process will be asked to leave the room during any such communications unless the patient allows them to be present. Efforts to maintain subject confidentiality will include following Federal Privacy Regulations which provide safeguards for privacy, security and authorized access. Except when required by law, subjects will not be identified by name, social security number, address, telephone number, or any other direct personal identifier in study records disclosed outside of Duke University Health System (DUHS). Subjects will not be revealed in any reports or publications resulting from this study. For records disclosed outside of DUHS, subjects will be assigned a unique code number. The paper and electronic data will be stored as per the RDSP
- Describe how research data will be stored and secured to ensure confidentiality:
  - The research data will be collected and stored utilizing the RedCap database approved by Duke Health System. Only appropriate personnel involved in the study will be given access to the database.

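### Only GI complications have a scheduled question, so the trial can speak to GI complications but not to the overall morbidity it expects the block to improve

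*Combined protocol and SAP*

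**What the plan says.** The Research Abstract states the hypothesis for the block: "we hypothesize that this approach will provide superior analgesia and improved morbidity" compared with direct wound injection. The Purpose of the Study repeats it.

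Design & Procedures fixes what is recorded. In hospital, "Subjects' verbal pain scores (NRS 11), opioid consumption, and GI complications will be recorded hourly for the first four hours", and then at 6, 12, 24 and 36 hours. One functional item is added: "On post op day 1 patients will be asked to ambulate a short distance of 50ft", with pain recorded during the walk. After discharge, patients are telephoned daily to day 7 and "asked the same questions they were asked during their hospital stay to asses opioid consumption, nausea/vomiting events, and GI complications". The Secondary Objectives define GI complications as bloating, nausea/vomiting and constipation.

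Risk/Benefit Assessment lists risks by technique in three frequency bands. For the block, the band at 10% or more reads "Nausea, fever, constipation". Its band from 2% to below 10% has 19 terms, ending with "anxiety, fall, temporary swelling, sensory loss, change in liver function tests, hiccups, respiratory depression, bruising".

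Data & Safety Monitoring adds a general duty: "PI will be monitoring all AEs and submitting reports to the IRB per DUHS IRB policy". Data Analysis and Statistical Considerations names opioid use, pain, GI complications, recovery and functional measures. It plans no comparison of adverse events between arms.

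**The concern.** The hypothesis is wider than the measurement. A trial that asks about GI symptoms at every contact, and about no other complication, can show a GI difference between the techniques. It cannot show whether a non-GI difference adds to it or offsets it. The protocol itself expects non-GI events with both techniques, and information not asked for on the daily calls cannot be recovered at analysis.

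Two things are at stake. A report of better morbidity with the block could rest on GI data alone. Non-GI events at home, in either arm, may also be recorded incompletely, because the calls do not prompt for them.

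**Working it through.** **1. Scheduled items.** From Design & Procedures: pain, opioid use, GI complications (including nausea/vomiting), and pain on the day-1 walk. Only one of these is a complication domain.

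**2. The two risk lists, by band.** Counted from Risk/Benefit Assessment.

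| Band | Block: listed (scheduled) | Infiltration: listed (scheduled) |
|---|---|---|
| 10% or more | 3 (2; fever is not) | 3 (3) |
| 2% to below 10% | 19 (0) | 12 (0) |

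**3. Unscheduled terms at 2% or more for at least one technique.** These are fever, the block's 19, and any terms from the infiltration 12 not already counted. Fatigue and tiredness are treated as one term.
- Higher band for the block: fever (10% or more against 2 to 10%), and six terms at 2 to 10% against below 2% (urinary retention, confusion, high blood pressure, sweating, anxiety, respiratory depression). That is 1 + 6 = 7.
- Listed only for the block: muscle twitching, taste disturbance, fall, sensory loss, liver-test change, hiccups, bruising. That is 7, so the block total is 7 + 7 = 14.
- Higher band or listed only for infiltration: dizziness, anemia, insomnia, muscle spasms, back pain. That is 5.
- Same band: fatigue/tiredness, headache, low blood pressure, itching, rapid heart rate, temporary swelling. That is 6.
- Check: 14 + 5 + 6 = 25. The block's 19 split as 6 + 7 + 6, and the infiltration 12 as 1 (fever) + 5 + 6.

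Bruising appears in two of the block's bands. It is counted once, in the higher one. If it belongs in the lower band, 14 becomes 13.

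**4. The scheduled GI terms.** Nausea and constipation are at 10% or more on both lists. Vomiting is at 10% or more for infiltration and is not on the block list. Bloating is on neither list.

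**5. Sample size.** The plan states 40 followed patients, alpha 0.05, 80% power and effect size 1.0. A two-sided t-test (sidedness assumed) needs 16.7 per arm. Dividing by the minimum Mann-Whitney relative efficiency, 16.7 / 0.864 = 19.3, gives 20 per arm, or 40 in total. Allowing 20% loss, 40 / 0.80 = 50. The plan's figures reproduce.

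**6. What 20 per arm could show if non-GI events were collected.** The documents give bands, not rates, so the rates below are assumed.

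| Assumed rates | Power, normal approximation | Power, exact Fisher | Per arm for 80% |
|---|---|---|---|
| 10% v 2% | 0.18 | 0.03 | 138 |
| 6% v 1% | 0.13 | 0.005 | 211 |
| 15% v 6% | 0.15 | 0.06 | 181 |

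The chance of seeing at least one event among 20 is 1 − (1 − p)^20. This is 18% at p = 1%, 33% at 2%, 71% at 6% and 88% at 10%. Collection would therefore yield a useful description, but not a test.

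**The case against.** The strongest reply is that no overall morbidity endpoint or composite is planned. The Background speaks of opioid-related morbidity, with nausea and vomiting as its example, and GI collection fits that. The investigator monitors all adverse events, nurses observe patients in the PACU, and 20 per arm could not test non-GI differences anyway. The primary outcome, 24-hour opioid use, is untouched.

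Much of this stands. It limits the point to secondary conclusions, makes any added collection descriptive, and supports narrowing the wording as an adequate alternative. It does not close the gap. A general monitoring duty sets no solicited items, no time points for asking and no report by arm, and the hypothesis as worded is not confined to opioid-related or GI effects.

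A reader might infer three stronger things that the documents do not support.
- *That the block's listed harms are never looked for.* Unsolicited capture is provided for. What is missing is a scheduled question.
- *That collection is tilted toward the block.* Non-GI harms are unscheduled in both arms, and five are weighted to infiltration. On the collected side, the lists differ only on vomiting, which the plan names jointly with nausea. The bands are not presented as a head-to-head comparison.
- *That the uncollected burden is about twice as large with the block.* At the bottom of each band, the block gives 20 × 0.10 + 19 × 0.02 × 20 = 9.6 expected events and infiltration gives 12 × 0.02 × 20 = 4.8. But at the top of its band infiltration approaches 12 × 0.10 × 20 = 24. The ranges overlap, so the ratio reflects list length and an assumed rate.

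**Conclusion.** The point holds as a mismatch between claim and measurement. GI complications are the only complication domain with a scheduled question. All 25 non-GI terms that the protocol lists at 2% or more for at least one technique lack one: 14 rank higher or appear only for the block, 5 for infiltration, and 6 are level. The trial as written can support a conclusion on GI complications, not on overall morbidity.

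The counts rest on a term-by-term reading of the lists, with fatigue and tiredness equated and bruising placed in its higher band. They show which events the plan anticipates. They do not show that either technique causes more harm, or that the comparison is biased in a known direction. The sample size and primary analysis are unaffected. The change is worth making before data collection because unasked questions cannot be answered later.

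**What to change.** At the existing in-hospital time points and daily calls, add a fixed yes/no checklist of the non-GI risks in Risk/Benefit Assessment, identical in both arms. Take in-hospital items from the chart. Liver-test change and anemia can be recorded only where routine care measures them. Pass every positive answer to the investigator as an adverse event, and report the items by arm beside the GI results as counts and percentages, without hypothesis tests.

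If the checklist is not added, replace the improved-morbidity wording in the Research Abstract and the Purpose of the Study with fewer GI complications, and confine the report's conclusions in the same way.

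The checklist costs an estimated minute or two per existing contact, a REDCap form change and one extra table. It needs no new visits and no change to sample size or to the day-7 end of follow-up. The wording alternative costs only a text amendment.

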we hypothesize that this approach will provide superior analgesia and improved morbidity when compared to direct injection of local anesthetic to the wound site.

- **Background & Significance:**

In 2014 in the United States there were approximately 17,107 kidney transplants performed (<https://www.kidney.org/news/newsroom/factsheets/Organ-Donation-and-Transplantation-Stats>). Of these a portion, approximately 6,000, were from living donors. Currently there is no consensus on the perioperative pain management strategies for these patients. Given the recent national attention to the ongoing opioid epidemic it seems appropriate to develop non-opioid pain management alternatives. Such strategies have been shown to decrease hospital stay and reduce morbidity associated with opioid use such as nausea and vomiting. Use of local anesthetics during surgery is a strategy currently utilized to reduce opioid use. In this study we aim at answering the question of whether direct wound infiltration of local anesthetic by the surgeon in the field is as effective as U/S guided Quadratus Lumborum regional block.

The Quadraus Lumborum block was described by Blanco *et. Al.* as a way to provide analgesia to truncal/intraabdominal procedures. Relatively recent case reports and studies have shown it to be an effective post-operative analgesic option for abdominal surgery. Patients undergoing donor nephrectomies here at Duke Medical Center are already receiving liposomal bupivacaine infiltration by the surgeon or QL blocks with liposomal bupivacaine placed by members of the regional anesthesia team. This study will simply utilize the already existing infrastructure to formally investigate if one technique provides better pain control. We hypothesize the ultrasound guided QL block with liposomal bupivacaine will offer superior post-operative analgesia than surgical field wound infiltration, using decreased 24-h post operative opioid totals. Additionally, as secondary endpoints we will also be examining differences in numerical pain scores post-operatively, GI complications (bloating, nausea/vomiting, constipation) as well as improved functionality of basic motor activities such as walking.

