- Chills, redness, slow heart rate, anxiety, urinary retention, tremor, dizziness when standing, tingling, fainting, high blood pressure, muscle weakness, neck pain, rash, sweating, arrhythmias, confusion, mood changes, respiratory depression, urinary incontinence, blurred vision, ringing in ears, allergic reaction

Patients will be monitored in the post-operative care unit by nurses assigned to their care. Patients will have post-operative analgesics available for pain control that include 25mcg IV fentanyl for pain scores for breakthrough pain and Tramadol PO 25-50 mg for pain scores 4-10/10 as described above.

Benefits include contributing to general knowledge base to improve future patient care. This includes potential confirmation of analgesic benefit, decreased pain scores, and improved patient satisfaction. Conversely, this study may show no benefit of the block, thereby invalidating the technique.

- **Cost to the Subject:**

Subjects will not incur any additional costs to participate in the study.

- **Data Analysis and Statistical Considerations:**

The primary hypothesis, that there is a difference in 24h opioid consumption between patients receiving an ultrasound guided regional block versus those receiving surgical field wound infiltration by the surgeon. We will also look at secondary outcomes evaluating numeric pain scores, GI complications (such as constipation and bloating and Nausea/Vomiting) and recovery between the two groups. Parametric and non-parametric data will be analyzed using t-tests, Chi-Squared, and Mann-Whitney tests as appropriate. If there is evidence of a difference in numeric pain score during the periods studied, we will perform post-hoc pair-wise multiple comparison corrected tests to identify the time-points where the intervention groups differ on pain score. Additional secondary analyses will assess differences in cumulative opioid consumption in IV morphine equivalents, numerical pain scores, and functional assays with parametric or non-parametric tests as appropriate. Statisticians employed by the Department of Anesthesiology will conduct these analyses.

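### The day-1 walking pain score exists only for patients who attempt the walk, and the plan does not record who did not walk or why

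*Combined protocol and SAP*

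**What the plan says.** Design & Procedures contains the only walking assessment. For the first post-operative day the text reads "patients will be asked to ambulate a short distance of 50ft and we will record pain levels using the numerical pain score reported during this" (the walk). It gives no field for whether the walk was attempted or finished, and no instruction for a patient who declines or cannot stand.

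Background & Significance names "improved functionality of basic motor activities such as walking" among the secondary endpoints. The Research Abstract also promises data on "ability to return to normal pre-surgery physical function levels", but no instrument is defined for it. The daily telephone calls after discharge cover opioid use, nausea/vomiting and GI complications, not walking.

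Data Analysis and Statistical Considerations will compare "numerical pain scores, and functional assays with parametric or non-parametric tests as appropriate". It has no rule for missing scores and defines no analysis set for this measure.

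**The concern.** Whether a walking score exists depends on something that happens after randomisation and may itself reflect the outcome. Too much pain is an obvious reason not to walk. Patients who do not start for that reason leave no score, so the average among those who walk is too favourable. If this happens more often in one arm, the comparison shifts towards that arm.

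There is a second loss that does not depend on pain. The endpoint is described as walking function, yet the one thing recorded is pain while walking. A patient who cannot walk is the clearest failure on a walking endpoint, and the plan has nowhere to count that failure. If the fact and the reason are not written down on day 1, later analysis cannot recover them.

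**Working it through.** **The plan's own figure.** The documents state no number for the walking score. The only relevant figure is the sample size, set for the primary outcome. A difference of 2 with effect size 1.0 implies SD 2/1.0 = 2. At two-sided 0.05 (sidedness is not stated), a t-test needs 17 per arm (80.7% power). Dividing by 0.864, the minimum relative efficiency of the Mann-Whitney test, gives 17/0.864 = 19.7, so 20 per arm and 40 in total. Then 40/(1 − 0.20) = 50. This reproduces the plan and is used below only to fix 20 per arm.

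**Assumptions, not in the documents.** True walking pain is the same in both arms, mean 5, SD 2. A fraction q of an arm does not walk. The tendency not to walk has correlation ρ with pain. At 20 per arm, 5%, 15% and 25% are 1, 3 and 5 patients.

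**Bias.** For a normal score, the mean among walkers is 5 − 2ρ·φ(z)/(1 − q), where z is the 1 − q normal quantile and φ the normal density. The factor φ(z)/(1 − q) is:

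- q = 5%: 0.1031/0.95 = 0.109
- q = 15%: 0.2332/0.85 = 0.274
- q = 25%: 0.3178/0.75 = 0.424

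At ρ = 1 (exactly the sorest patients do not walk) the walkers' means are 4.78, 4.45 and 4.15. The false differences are:

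| Not walking | ρ = 1 | ρ = 0.5 | ρ = 0 |
|---|---|---|---|
| 25% v 5% | 0.63 | 0.32 | 0 |
| 15% v 5% | 0.33 | 0.17 | 0 |

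Simulation with scores rounded to whole numbers from 0 to 10 gives 0.63 and 0.32 at ρ = 1, and 0.32 and 0.16 at ρ = 0.5. If non-walkers have less pain than walkers (ρ = −0.3, 25% v 5%), the sign reverses: 2 × 0.3 × (0.424 − 0.109) = 0.19 points against the arm with more non-walkers.

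**Effect on the test.** Simulated trials had 20 per arm, equal true pain, a Mann-Whitney test and 4,000 runs per row. Arm A has at least as many non-walkers as arm B. Without bias, a significant result favouring A should occur in 2.5% of trials. Worst rank means every non-walker is ranked below every walker.

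| Not walking A v B, ρ | Mean A − B, walkers only | Favours A, walkers only | Favours A, worst rank | Favours B, worst rank |
|---|---|---|---|---|
| 20% v 5%, 0.5 | −0.23 | 4.6% | 0.8% | 7.3% |
| 20% v 5%, 0.8 | −0.39 | 8.1% | 1.1% | 5.3% |
| 30% v 5%, 0.5 | −0.38 | 7.0% | 0.2% | 15.4% |
| 30% v 5%, 0.8 | −0.63 | 14.3% | 0.4% | 10.4% |
| 30% v 5%, 0 | −0.01 | 2.7% | 0.1% | 27.5% |
| 10% v 10%, 0.7 | 0.01 | 2.3% | 2.6% | 2.2% |

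If arm A is truly 1 point worse (30% v 5%, ρ = 0.8), the walkers-only difference shrinks to 0.36 and is detected in 7% of trials, against 44% with worst ranking. The ρ = 0 row shows what worst ranking measures: it responds to completion even when pain is equal, so it answers a mixed question.

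**The case against.** The strongest reply is that the problem may be small or absent. These are ASA 1-2 donors described as having few or no co-morbidities, so nearly all may walk 50 ft. No rate in the documents supports 25%. At ρ = 0.5 with 15% v 5%, the shift of about 0.17 points is small beside a standard error of 2·√(2/20) = 0.63, and equal rates give no bias. Pain is also recorded at 24 and 36 hours whether or not the patient walks. All of this stands and limits the size of the point. It does not supply the missing walking result.

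A reader might infer that the arm with more non-walkers always looks better. The calculation does not support that. It requires non-walking to track higher pain. For patients who are weak but not sore, the pain comparison is roughly unbiased and can even reverse.

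A reader might also infer that the block arm in particular will be flattered, because Risk/Benefit Assessment lists "decreased mobility, muscle spasms, muscle weakness or pain" for the nerve block. Those entries are in the rare band, below 2%, which is under 20 × 0.02 = 0.4 patients per arm for each. Falls and sensory loss are listed only for the block, at 2% to under 10%, but neither is the same as being unable to walk. The infiltration list also contains muscle weakness and fainting (both rare), and dizziness at 2% to under 10%. The lists do not clearly predict which arm will have more non-walkers.

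Nor do the documents say that a patient who starts and stops has no score. Such a patient can report pain during the attempt. Only those who never start must lack one.

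Finally, this is a low-tier endpoint. The list under Secondary Objectives, introduced there as exploratory, omits walking; only Background & Significance calls it a secondary endpoint.

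**Conclusion.** The point holds in conditional form. The plan has a walking endpoint but records nothing for a patient who does not walk. If not walking goes with higher pain and its frequency differs between arms, a walkers-only comparison makes the arm with more non-walkers look better than it truly is, though not necessarily better than the other arm. The size is about 0.2 to 0.6 points under assumed rates of 5% v 15-25%, with mean 5, SD 2 and correlation 0.5 to 1. If not walking is unrelated to pain, mean pain is unbiased and the harm is that failed walks go uncounted.

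The documents are silent on non-walkers. They do not state that such patients are excluded, and the actual rate is unknown. The 24-hour opioid outcome and the pain scores at scheduled times do not depend on walking, so the main conclusion of the trial is not at risk. The change is still worth making because it is nearly free and the information cannot be recovered later.

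**What to change.** In Design & Procedures, record for every patient whether the 50 ft walk was attempted, whether it was completed, the pain score during any attempt (including one that stops early), and the reason for not completing.

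In Data Analysis and Statistical Considerations, report the percentage completing the walk by arm as the walking-function result, next to the walkers' pain score. Add one prespecified sensitivity analysis: a Mann-Whitney test that ranks every patient who could not complete the walk, whatever the reason, below every completed walk. Applying one rule to all reasons leaves no category unhandled and avoids a judgement about cause deciding a patient's rank.

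The cost is two or three form fields at an assessment already planned, and a sentence or two of analysis text. The drawback is that the rank analysis mixes completion with pain, so it should supplement the walkers' score and not replace it.
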